5. TRIAL OBJECTIVES AND PURPOSE

The rationale of this study is to understand a subject's experience and satisfaction after treatment with A-101 40% and how that correlates with a healthcare provider's assessment based on PLA score.

Aclaris Therapeutics, Inc. recently completed three phase III clinical studies (301, 302, and 303) that demonstrated the safety and efficacy of A-101 40% in treating Seborrheic Keratoses.

5.1. Objective

The objective of this study is to assess subject satisfaction after treatment with A-101 40% on SKs of the face, neck, and décolletage.

6. INVESTIGATIONAL PLAN

6.1. Overall Study Design

This study is an open-label study designed to evaluate subject's satisfaction after treatment of seborrheic keratoses with A-101 40%. The subject's treatment application will be documented via a series of photographs to aid in the assessment of the treated SK and to mimic real-world treatment environment.

Dermatologists (investigators) will identify 3 eligible target SKs on each subject; 2 target SKs must be on the face, and the additional 1 target SK must be on the neck or décolletage. Up to 4 additional non-target SKs may be identified on the face, neck or décolletage. Each target and non-target SK will be treated during up to 3 separate treatment visits: Visit 2, Visit 5, and Visit 7. Each SK must be treated by a study trained healthcare provider at the site. Retreatment of identified target and non-target SKs will be determined by the physician using the Physicians Lesion Assessment Scale (PLA). Target and non-target SKs that have been assigned a PLA of ≥ 1 will be treated on Day 15 and Day 29. Each treatment visit requires up to 4 applications of A-101 (Hydrogen Peroxide) Topical Solution, 40% (w/w) to each eligible target and non-target SK. Each application will last up to 20 seconds with about 60 seconds between applications.

A total of 30 subjects will be enrolled. A trained photographer will document each subject's target and non-target SKs at every visit. During Visit 2, subjects will have photographs taken of each SK at specified post treatment timepoints.

Subjects will be assessed for adverse events related to A-101 40% throughout the conduct of the study.

Subjects will be required to complete a total of 11 study visits. The protocol defined study visits are:

- Visit 1 (Day -13 - 0) Screening
- Visit 2 (Day 1) Study Medication Treatment
- Visit 3 (Day 2) Follow-up Visit
- Day 4 (Day 8) Follow-up Visit
- Visit 5 (Day 15) Study Medication Treatment (if PLA ≥ 1)
- Visit 6 (Day 22) Follow-up Visit
- Visit 7 (Day 29) Study Medication Treatment (if PLA ≥ 1)
- Visit 8 (Day 36) Follow-up Visit
- Visit 9 (Day 57) Follow-up Visit
- Visit 10 (Day 85) Follow-up Visit
- Visit 11 (Day 113) Follow-up Visit; End of Study

Refer to Table 3: Study Design and Schedule of Assessments for a complete list of protocol required study assessments.

6.2. Number of Subjects

A total of 30 subjects will be treated on the study at 3 investigational sites in the US.

6.3. Treatment Assignment

This is an open-label study.

6.4. Dose Adjustment Criteria

If a subject refuses the initial treatment or retreatment, the investigator must report the visit number, visit date, target SK number(s) that the subject refused to allow treatment for and the reason for the refusal in the subject's CRF.

If the subject's refusal is associated with an AE, the investigator must also report the event on the appropriate CRF.

The subject must have the Visit 2 initial study medication treatment to all target SKs to remain in the study.

The subject does not need to be removed from the study based solely on her/his refusal to have a study medication retreatment at Visit 5 or Visit 7.

Table 3: Study Design and Schedule of Assessments

Visit	Visit 1	Visit 2	Visit 3	Visit 4	Visit 5	Visit 6	Visit 7	Visit 8	Visit 9	Visit 10	Visit 11
Treatment Day	Day -13 - 0	Day 1	Day 2	Day 8	Day 15	Day 22	Day 29	Day 36	Day 57	Day 85	Day 113
Visit Window	N/A	N/A	N/A	± 1 day	± 1 day	± 1 day	± 1 day	± 1 day	± 7 days	± 7 days	± 7 days
Informed Consent	X										
Inclusion/ Exclusion ¹	X	X									
Subject Identifier ²	X										
Dermatological Medical History	X										
Demographics	X										
Fitzpatrick Skin Type Assessment ³	X										
Vital Signs ⁴	X	X			X		X			X	X
Prior Medications/Therapies ⁵	X										
Target and Non-Target SK Identification ⁶	X										
Physician’s Lesion Assessment ⁷	X	X	X	X	X		X			X	X
SK Dimensions ⁸	X	X	X	X	X		X			X	X
SK Photography ⁹	X	X ¹⁰	X ¹¹	X	X ¹⁰	X	X ¹⁰	X	X	X	X
Study Medication Application ¹²		X			X		X				
Subject Satisfaction Assessment ¹³		X	X			X		X		X	X
Concomitant Therapies ¹⁴	X	X	X	X	X	X	X	X	X	X	X
Adverse Events ¹⁵		X	X	X	X	X	X	X	X	X	X

¹Subject inclusion/exclusion criteria will be reassessed prior to enrollment during Visit 2.

Protocol A-101-SEBK-402

²Investigational sites will assign a unique five-digit subject identifier to each subject at Visit 1, formatted as NN-NNN where the first 2 digits are the site number, and the final 3 digits are the subject number that must be assigned in ascending numerical order (using leading zeroes, as appropriate). This subject identifier will be used in all study documentation for the duration of the study.

³Each subject's skin must be assessed during Visit 1 using the Fitzpatrick Skin Type Assessment. Refer to Table 6 for the scale.

⁴Vital signs [including temperature, pulse, respiratory rate, blood pressure, height and weight (Visit 1 only)] will be measured by a qualified staff member at Visit 1, Visit 2, Visit 5, Visit 7, Visit 10, and Visit 11.

⁵Prior medications/therapies will be collected for a time-period of 13 days prior to Visit 1. Refer to Section 8.4 for a list of permitted and restricted concomitant medications.

⁶The treating investigator will identify 3 target SKs and up to 4 non-target SKs. Two (2) target SKs must be on the face, and the additional 1 target SK must be on the neck or décolletage. The 4 non-target SKs may be located on the face, neck, or décolletage.

⁷The investigator will use the Physician's Lesion Assessment (PLA) to assess the severity of each target and non-target SKs at Visits 1, 2, 3, 4, 5, 7, 10, and 11. At Visit 2, Visit 5 and Visit 7, the investigator must assess each target and non-target SK prior to application of the study medication. In order to be eligible for enrollment to the study during Visit 2, the subject must have a PLA grade ≥ 2 for each target and non-target SK.

⁸The investigator will measure the dimensions of each target and non-target SK at Visits 1, 2, 3, 4, 5, 7, 10 and 11. At Visit 2, Visit 5 and Visit 7, the investigator must measure each target and non-target SK prior to application of the study medication. In order to be eligible for enrollment to the study during Visits 1 and 2, each target SK must have a diameter that is between ≥ 5 and ≤ 15 mm (inclusive) and be raised. In order to be eligible for enrollment to the study during Visits 1 and 2, each non-target SK must be a raised SK. At Visits 3, 4, 5, 7, and 10 the investigator must assess the thickness of each target and non-target SK above the surrounding skin. Additional target and non-target SK requirements are outlined in Section 10.1 .

⁹Each target and non-target SK will be photographed at all study visits using the Aclaris Therapeutics, Inc. supplied photography equipment.

¹⁰During Visit 2 each target and non-target SK will be photographed prior to the application of A-101 40%, 10 minutes post application (+2 minutes), and 1-hour post application (± 10 minutes). During Visit 5 and Visit 7, the target and non-target SKs will be photographed prior to the application of A-101 40%, if applicable.

¹¹During Visit 3 each target and non-target SK will be photographed 24-hours post application during Visit 2 (± 2 hours).

¹²A-101 40% will be applied to each target and non-target SK by a study trained healthcare provider at the site. Each target and non-target SK will be treated with A-101 40% following confirmation of subject eligibility and study enrollment at Visit 2. If a target or non-target SK meets the criteria for retreatment as defined in Section 9.5, the SK will be retreated at Visit 5 and Visit 7. Following application of A-101 40%, subjects must NOT wash/submerge a target and non-target SK for at least 6 hours and they must NOT apply any topical products to any target or non-target SK for at least 6 hours.

¹³Subjects will be asked to assess how satisfied they are with the treatment experience they received for the target and non-target SKs at the specified visits. On Visit 2 the subject will complete the assessment prior to application of A-101 40%. On Visit 3 the subjects will complete the assessment approximately 24 hours after the treatment. On Visit 6 and Visit 8 the subjects will complete the assessment approximately 1 week after the treatment, only if the subject received treatment on Visit 5 or Visit 7. The subject will complete the assessment during the Visit 10 and Visit 11.

¹⁴All concomitant therapies including (topical and oral) prescription medications, over the counter medications, natural supplements and non-drug therapies including chiropractic, physical therapy, and energy-based therapy must be documented in the subject CRF. Subjects must not apply any topical products (*e.g.*, moisturizers, sunscreen, etc.) to their target and non-target SKs within 12 hours prior to any study visit.

¹⁵The reporting period for SAEs begins when the subject signs the informed consent form. Refer to Section 11.6 for instructions on the reporting of SAEs. Non-serious clinical adverse events will be collected following the application of the study medication at Visit 2 and continue through Visit 11. All safety reporting (AEs and SAEs) will conclude at Visit 11.

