7.5. Subject Replacement

If a subject is enrolled to the study but does not receive a dose of study drug, then the subject may be replaced.

Subjects that are determined to be screen failures may be rescreened for the study and if determined to be eligible for the study they may be enrolled using the same subject identifier and must sign a new informed consent form.

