9.5. Administration

The subject will receive up to 4 applications to each target or non-target SK at Visit 2, and if the subject meets retreatment criteria, at Visit 5 and Visit 7.

Apply study medication to each target and non-target SK for approximately 20 seconds. Allow each target and non-target SK to remain undisturbed for approximately 60 seconds. Repeat the application/waiting cycle until the study medication has been applied to each target and non-target SK up to 4 times. Subjects may receive up to 3 treatments (Visit 2, Visit 5 and Visit 7).

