10.1. Target SK Identification

At Visit 1, the investigator will identify up to 7 Seborrheic Keratoses on each subject for treatment and evaluation. Three (3) target lesion must be identified, and up to 4 non-target lesions may be identified. Two (2) target SKs must be on the face, and the additional 1 target SK must be on the neck, or décolletage. Up to 4 additional non-target lesions may be on the face, neck, or décolletage.

Face:

- Vertically from the mandibular ridge vertically up to the hairline (for subjects with a receded hairline the hairline is defined by the vertical line drawn coronally from tragus to tragus)
- Horizontally from tragus to tragus, excluding the eyelids and areas within 5mm of the orbital rim.

Neck:

- Vertically from the mandibular ridge vertically down to the top of the collar bone

Décolletage:

- From the collar bone down including the shoulders and cleavage area

At Visit 1, each target SK must:

- Have a clinically typical appearance
- Have a PLA of ≥ 2
- Have a diameter between 5 to 15 mm
- Be a discrete lesion (no overlapping lesions)
- Not be covered with hair which, in the investigator's opinion, would interfere with the study medication treatment or the study evaluations (NB: the study medication may bleach hair)
- Not be in an intertriginous fold
- Not be on the eyelids
- Not be within 5mm of the orbital rim
- Not be pedunculated.

At Visit 1, each non-target SK must:

- Have a clinically typical appearance

[figure not shown]
- Have a PLA of ≥ 2
- Be a discrete lesion (no overlapping lesions)
- Not be covered with hair which, in the investigator's opinion, would interfere with the study medication treatment or the study evaluations (NB: the study medication may bleach hair)
- Not be in an intertriginous fold
- Not be on the eyelids
- Not be within 5mm of the orbital rim
- Not be pedunculated.

Record the approximate location of each target and non-target SK on the body chart in the CRFs. Number the target SK starting with 1 and proceeding up to 3 with no number omitted or reused. The target SKs on the face should be numbered 1 and 2, and the additional 1 SK on the neck and/or décolletage should be numbered 3. The non-target SKs should be numbered 4-7 starting with 4 and proceeding up to 7 with no number omitted or reused.

Aclaris Therapeutics, Inc. will provide the investigational site with standard circular templates and colored stickers that are to be used to identify the target and non-target SKs.

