#### **1.1.1 Primary Objective**

Subject satisfaction after treatment with A-101 (Hydrogen Peroxide) topical solution, 40% (w/w) at Day 85 and Day 113.

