#### **3.2 ANALYSIS POPULATION AND DISPOSITION OF SUBJECTS**

##### **3.2.1 Data Sets Analyzed**

Intent-to-Treat (ITT) analysis set includes all enrolled subjects. This is the analysis set for all analyses. A subject is considered enrolled if at least one study treatment is applied.

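### Protocol 6.4 takes dosed subjects with any target SK untreated at Visit 2 out of the study, so they stay in ITT but give no satisfaction data

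*Protocol*

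**What the plan says.** Each subject has three target SKs and may have more lesions treated: "Three (3) target lesion must be identified, and up to 4 non-target lesions may be identified" (Protocol 10.1). Protocol 6.4 makes continued participation depend on the first session: "The subject must have the Visit 2 initial study medication treatment to all target SKs to remain in the study". The rule names target SKs only. The same section is more permissive about the later sessions (Visits 5 and 7): "The subject does not need to be removed from the study based solely on her/his refusal to have a study medication retreatment". Refusals must be recorded with the SK numbers and the reason, and "If the subject's refusal is associated with an AE, the investigator must also report the event on the appropriate CRF".

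Protocol 9.5 sets an upper limit on applications but no minimum: "The subject will receive up to 4 applications to each target or non-target SK at Visit 2".

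On who counts, SAP 3.2.1 puts all enrolled subjects in the ITT set and adds: "A subject is considered enrolled if at least one study treatment is applied". Protocol 7.5 limits replacement to undosed subjects: "If a subject is enrolled to the study but does not receive a dose of study drug, then the subject may be replaced".

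The primary objective in SAP 1.1.1 is "Subject satisfaction after treatment with A-101 (Hydrogen Peroxide) topical solution, 40% (w/w) at Day 85 and Day 113". Under footnote 13 of the schedule of assessments, the Visit 2 survey is completed before application and the first post-treatment survey comes at Visit 3, about 24 hours later. Protocol 7.4 asks for the reason and date of withdrawal, plus monitoring where the reason is an AE. It specifies no exit survey. SAP section 3 covers PLA and safety only and leaves satisfaction to a separate analysis plan, which is not among the documents.

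**The concern.** The study asks how satisfied people are after treatment, including with the treatment experience itself (a separate item in the end-of-study questionnaire). Refusing a further target SK during the first session can be an expression of that experience. Where it is, the 6.4 rule ends data collection because of something closely related to the primary outcome, and the remaining subjects are partly selected for having accepted the first session. There is no control arm in which the same selection could operate and cancel out.

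The loss is also avoidable. Section 6.4 already keeps subjects who refuse retreatment, so the study can follow people who are incompletely treated. Satisfaction not asked about cannot be recovered at analysis. The rule costs safety data too: an exposed subject leaves before the non-serious AE collection that otherwise runs to Visit 11, apart from the monitoring that 7.4 provides when the withdrawal is for an AE.

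**Working it through.** The plan has no figure to reproduce here. The sample size of 30 is given without a precision target, power, effect size or dropout rate. The check is a trace through the text, followed by an illustration of size.

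**Trace of one subject: two target SKs treated at Visit 2, the third refused**

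| Question | Source | Answer |
|---|---|---|
| Stays in the study? | Protocol 6.4 | No |
| In the ITT set? | SAP 3.2.1 | Yes, on the plain reading that a treatment has been applied |
| Replaceable? | Protocol 7.5 | No, a dose was given |
| Any post-treatment survey? | Schedule footnote 13; Protocol 7.4 | None |
| Day 85 and Day 113 satisfaction? | Follows from the above | Missing |
| Handling of the missing value? | SAP section 3 | Not stated; satisfaction is left to another plan |

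**Size if it happens**

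Let N = 30 treated subjects, x of whom would be satisfied, and k removed subjects, all dissatisfied. Dropping the k subjects changes the proportion from x/N to x/(N − k), a rise of (x/N) × k/(N − k). Take x = 24. This is an assumption, since the documents define no satisfied threshold and give no satisfaction rate.

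- k = 0: 24/30 = 80.0%
- k = 1: 24/29 = 82.8%, a rise of 2.8 points
- k = 2: 24/28 = 85.7%, a rise of 5.7 points
- k = 3: 24/27 = 88.9%, a rise of 8.9 points

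With k = 1 and other satisfaction levels, the rise runs from 14/29 − 14/30 = 48.3% − 46.7% = 1.6 points to 26/29 − 26/30 = 89.7% − 86.7% = 3.0 points. On the 1-to-5 item, with a retained mean of 4.0 and the removed subject scored 1, the mean over all treated is (29 × 4.0 + 1)/30 = 3.9, a difference of 0.1.

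The direction depends on the assumption. If the one removed subject would have been satisfied, the observed figure is 23/29 = 79.3%, which is 0.7 points below 80.0%.

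**How often it might happen**

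The documents give no rate of refusal at a first session. The nearest figure is from study A-101-SEBK-303 (open-label, up to 4 applications), where 0 of 147 subjects discontinued for an AE. The one-sided 95% upper limit is 1 − 0.05^(1/147) = 2.0%. For an assumed per-subject rate q, the chance of at least one case among 30 is 1 − (1 − q)^30:

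| q | Expected cases (30q) | Chance of at least one |
|---|---|---|
| 1% | 0.3 | 26% |
| 2% | 0.6 | 45% |
| 5% | 1.5 | 79% |
| 10% | 3.0 | 96% |

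At q = 2%, the chance of two or more is about 12% and of three or more about 2%. AE discontinuation is not the same event as refusal. In the same study 5 of 147 (3.4%) withdrew consent, with reason and timing not stated. If every one of those were treated as a first-session refusal, the expected number here would be 30 × 5/147 = 1.0. Zero or one subject is therefore the most likely range.

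**The case against.** The strongest reply is that a minimum first exposure is a defensible requirement in a study of satisfaction after treatment, and that the event is rare. Rarity stands, and it limits the size. The exposure argument is weaker, because a subject with one or two SKs treated has been exposed and has an experience to report.

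Three stronger readings are tempting, and the documents do not support them.

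- *Every subject who stops part-way through Visit 2 is removed.* The rule covers target SKs only, so stopping during the non-target SKs does not trigger it. There is no minimum number of applications, and Protocol 8.5.2 accepts treating SKs in rotation. A subject who stops after each target has had one application has arguably had all targets treated and stays.
- *The rule filters out those with the worst experience.* This is an inference. Refusal can have other causes, which is why 6.4 requires the reason. Subjects who dislike the session but complete the targets are kept, as are those who refuse retreatment.
- *The ITT definition is wrong, or hides the loss.* Keeping exposed subjects in the ITT set is normal and proper for safety. SAP 3.2.2 reports discontinuations by reason, and SAP 3.6 tabulates subjects by number of lesions treated at each visit, so such cases would be visible. The satisfaction denominator belongs to a plan that cannot be seen here, so a biased primary analysis cannot be asserted.

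One further objection stands and shapes the fix. Protocol 8.5 has all identified SKs with PLA of at least 1 re-treated at Visits 5 and 7. A target SK never treated enters with PLA of at least 2, so keeping the subject brings that text into play for a lesion with no first treatment. The change is thus not entirely separate from treatment and needs reconciling.

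**Conclusion.** The point holds in limited form. Protocol 6.4 ends collection of the primary outcome for a dosed subject with any target SK untreated at Visit 2, while that subject remains in ITT and cannot be replaced. No available document says how the missing satisfaction data are handled.

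The loss is informative, and favours the product, only if the refusal reflects a poor experience. The likely size is 0 to 1 subject, or about 3 points on a satisfied proportion. That rests on an assumed 80% satisfied among 30, removed subjects being dissatisfied, and AE discontinuation serving as a rough proxy for refusal. The effects of 6 and 9 points need two or three removals and are unlikely on that proxy.

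This does not undermine the study. It is a worthwhile, low-cost improvement to a stated rule, best made before data are lost.

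**What to change.** 1. **Protocol 6.4.** Amend it so that a subject with at least one SK treated at Visit 2 stays in follow-up for the scheduled satisfaction surveys, PLA and safety, whether or not all target SKs were treated. Recording of refusals and reasons stays as it is. Subjects remain free to withdraw consent.
2. **Satisfaction analysis plan.** Use all treated subjects as the denominator at Day 85 and Day 113, report the number of subjects with incomplete Visit 2 treatment and the reasons, and add a sensitivity analysis counting those without data as not satisfied.
3. **PLA analyses.** Flag SKs not treated at Visit 2 in the lesion-level summaries and per-subject averages, and give a summary that excludes them.
4. **Reconciliation.** The sponsor must reconcile 6.4 with the retreatment text in 8.5 for SKs never treated. No treatment rule is proposed here. SAP 3.2.1, which defines enrolment by treatment applied, should also be aligned with Protocol 7.5, which allows a subject to be enrolled without a dose.

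The cost is a short protocol amendment, small edits to both analysis plans, a few flagged lesions in the PLA tables, and possibly a slightly lower reported satisfaction.

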7. SELECTION AND WITHDRAWAL OF SUBJECTS

7.1. Subject Inclusion Criteria

Subjects must meet all the following criteria to be considered for participation in this study:

1. Subject can comprehend and is willing to sign an informed consent for participation in this study.
2. Male or female between the ages of 30 and 75 years old.
3. Subject has a clinical diagnosis of stable clinically typical Seborrheic Keratosis.
4. Subject has 3 eligible Seborrheic Keratoses; 2 target SKs must be on the face, and the additional 1 target SK must be on the neck or décolletage. Each target SK must meet the following requirements:
 - a. Have a clinically typical appearance
 - b. Have a Physician's Lesion Assessment of ≥ 2
 - c. Have a diameter between 5 to 15 mm
 - d. Be a discrete lesion (no overlapping lesions)
 - e. Not be covered with hair which, in the investigator's opinion, would interfere with the study medication treatment or the study evaluations
 - f. Not be in an intertriginous fold
 - g. Not be on the eyelids
 - h. Not be within 5mm of the orbital rim
 - i. Not be pedunculated
5. Subject may have up to 4 additional non-target Seborrheic Keratoses on the face, neck or décolletage treated. Each non-target SK must meet the following requirements:
 - a. Have a clinically typical appearance
 - b. Have a Physician's Lesion Assessment of ≥ 2
 - c. Be a discrete lesion (no overlapping lesions)
 - d. Not be covered with hair which, in the investigator's opinion, would interfere with the study medication treatment or the study evaluations
 - e. Not be in an intertriginous fold
 - f. Not be on the eyelids
 - g. Not be within 5mm of the orbital rim
 - h. Not be pedunculated
6. Subjects must have had cryosurgery for SK removal within the last 6 months and prior to first treatment with A-101 (Hydrogen Peroxide) Topical Solution, 40% (w/w).
7. Target and non-target SKs must not have been previously treated.
8. Subject is in good general health and free of any known disease state or physical condition which, in the investigator's opinion, might impair the evaluation of any target or non-target SK or which exposes the subject to an unacceptable risk by study participation.
9. Subject is willing and able to follow all study instructions and to attend all study visits.

